1. CLINICAL PROTOCOL

1.1 Background

Our study aims to determine the efficacy of the MAESTRO Cochlear Implant in patients with postlingual, single-sided deafness. Single-sided deafness can arise from base of skull/temporal bone fractures leading to hearing loss, infection such as meningitis or labyrinthitis, vascular disease affecting the inner ear, Ménière's disease, or sudden sensorineural hearing loss, each of which prevents the faithful transmission of auditory information from the cochlea to the brainstem. Patients with single-sided deafness may also suffer from tinnitus in the affected ear, which can be debilitating. Unlike current treatments for single sided deafness, cochlear implantation has the potential to improve hearing abilities and suppress tinnitus in these patients.

Many patients with single-sided deafness experience difficulty hearing in the setting of background noise, impaired sound localization and tinnitus. These symptoms can affect communication in social settings, causing psychosocial stress and resulting in a decreased quality of life. Treatment options for single sided deafness in the United States include the contralateral routing of signals (CROS) hearing aid and the implantable bone conduction hearing aid. These devices take sound from the affected ear and transmit it to the unaffected ear. Although these options can improve sound and speech awareness on the deaf side, studies have shown that use of these devices does not significantly improve sound localization and does not address the issue of tinnitus in the deaf ear. Recently, several European studies have shown that cochlear implantation can improve both perceived hearing ability and measured speech comprehension and localization in adult and pediatric patients with unilateral hearing loss. Furthermore, many patients experience tinnitus suppression following cochlear implantation. These clinical data suggest that cochlear implantation provides clinical benefits not seen with the CROS or bone-conduction devices.

Massachusetts Eye and Ear Infirmary

SUPP M - Clinical Trial Template

1.2 Rationale

Single-sided deafness (SSD) afflicts approximately 60,000 new patients per year in the United States (Popelka et al., 2010). The most common causes of these single-sided losses are sudden sensorineural hearing loss, Ménière's disease, trauma, infections, and vascular insults. Patients with SSD face significant difficulty with sound localization and communicating in the presence of background noise (Bishop and Eby, 2010; Kamal et al., 2012). Tinnitus is another significant problem for some SSD patients; this can be incapacitating and no available effective therapies exist outside of cochlear implantation (Arts et al., 2012). Difficulty hearing in background noise and increased tinnitus can lead to significant frustration in social situations and contribute to increased isolation and a decreased quality of life.

In the United States, options to treat SSD have included contralateral routing of signals to the hearing ear via (CROS) hearing aids and the bone-anchored hearing aid (BAHA) system, an osseointegrated device that provides direct transcranial stimulation of the contralateral side. For SSD, the BAHA appears to outperform other types of CROS aids (Niparko et al., 2003). Indeed, the BAHA provides some benefit to SSD patients, as measured both by subjective patient reports and an improvement on hearing-in-noise tests. However, these aids are unable to provide information regarding sound localization, even after long-term use (Nicolas et al., 2012; Snapp et al., 2012; Linstrom et al., 2009; Niparko et al., 2003). SSD patients using the BAHA do, moreover, continue to suffer significant deficits on hearing-in-noise testing relative to normal hearing adults (Linstrom et al., 2009). Taken as a whole, data supporting the use of the BAHA in SSD suggest that while SSD patients derive some benefit from the device, this benefit is limited.

Tinnitus is another problem experienced by a significant fraction of SSD patients. While the precise neural substrates of tinnitus remain to be elucidated, hearing loss is highly correlated with the development of ipsilateral tinnitus. Current treatment strategies for tinnitus involve cognitive behavioral therapy in conjunction with optimization of aural inputs (Arts et al., 2012) and, in some cases, antidepressant therapy. As SSD patients have by definition lost useful hearing on one side, optimizing input on that side is not useful. The treatment of tinnitus in SSD patients has therefore been limited to helping these patients deal with the symptom rather than addressing the root cause of the problem.

To directly address the tinnitus experienced by SSD patients by increasing signal through the cochlear nerve, several groups have carried out cochlear implantation (Arts et al., 2012). These results have been promising, with 80-95% of patients in the largest series finding improvement in their tinnitus or even, in a fraction of cases, complete tinnitus suppression. In nearly all cases, this effect is dependent on signal from the cochlear implant, supporting the idea that decreased input from the cochlear nerve contributes to the development of tinnitus (Van de Heyning et al., 2008; Arndt et al., 2010; Ramos et al., Kleine Punte et al., 2011).

Cochlear implantation in SSD patients has also resulted in significantly improved sound localization and ability to hear in noise (Kamal et al., 2013). One important study examined SSD patients who were treated with cochlear implantation; the untreated side was either normal or treated with a hearing aid. The data demonstrated that, although there was a significant benefit in speech understanding and subjective quality of sound, sound localization only improved in patients with normal hearing on the opposite side (Vermeire and Van de Heyning, 2009). These findings are consistent with a more recent pilot study, in which three patients with short-term SSD and normal hearing in the other ear received a cochlear implant on the deafened side. These patients all achieved open-set speech recognition, improved sound localization, and improved word recognition in noise (Firszt et al., 2012). Another critical study evaluated SSD patients who had undergone cochlear implantation, comparing use of the cochlear implant to a CROS or BAHA. This study found that cochlear implantation resulted in significant gains with respect to objective sound localization and hearing-in-noise testing relative to the CROS or BAHA device in the same patients. Subjective and quality of life measures were also significantly improved with use of the implant (Arndt et al., 2010). Taken together, early data indicate that cochlear implantation in SSD can result in significant tinnitus suppression, improved sound localization and hearing-in-noise, and better quality of life overall.

2 Our hypotheses are that adult patients with postlingual, single-sided deafness who undergo cochlear implantation will 1) wear the implant full-time, 2) report that the cochlear implant provides benefit, 3) show improvement in speech comprehension in quiet and in background noise, 4) demonstrate an improvement in sound localization, and 5) report a reduction in the frequency and intensity of tinnitus compared to before

surgery. To test these hypotheses, we will formally and systematically test patients both before and after surgery as detailed below.

2. STUDY OBJECTIVES

2.1 Primary Objective

The primary objective of this study is to better assess the efficacy of cochlear implants in enhancing hearing abilities in patients with single sided deafness. The parameters being assessed include hearing in background noise, sound localization, tinnitus suppression, and overall quality of life. Our study will address several specific aims including:

Aim 1: Determine the audiologic outcomes following CI surgery for single sided deafness.

We will implant ten adult patients with postlingual single sided deafness with the MED-EL MAESTRO CI with Flex 28 electrode array using a round window insertion approach. Intraoperative imaging with a reverse Stenver xray will be performed to confirm proper electrode placement. We will assess sound-field thresholds for the cochlear implant alone and word recognition ability in the monoaural and binaural condition. We will also have patients complete the following questionnaires: 1) Hearing Handicap Inventory for adults, 2) Abbreviated Profile of Hearing Aid Benefit and 3) Speech, Spatial, and Qualities of Hearing Scale (SSQ)(Noble and Gatehouse, 2006) prior to and after implantation to assess subjective benefit outcomes. Finally, we will document the reported frequency of implant use and the use settings of the implant.

Aim 2: Determine the spatial hearing benefits following CI surgery for single sided deafness.

The bilateral benefits of understanding speech-in-noise will be evaluated in collaboration with [name] at the University of Wisconsin. Briefly, subjects will be flown to Madison and undergo spatial hearing testing in [name] lab pre- and post-operatively. Funding from [name] lab will cover all costs for travel, accommodations and meals for the subject and one travel companion. Subjects will be their own control and testing will take place at time points before and after surgery. They will be tested with the acoustic ear alone before the CI surgery. Following CI surgery, testing will be done with the bilateral condition and with the acoustic ear alone. On one task, subjects will identify a single

word randomly chosen from a set of fifty possible alternatives and presented from a loudspeaker directly in front of the subject. Speech intelligibility will be tested by masking sentences co-presented at different spatial configurations (-90° or +90°). The presentation level of the target speech will be varied in order to generate different signal-to-noise-ratios at each condition. We will evaluate implanted SSD patients with the device turned on and off to directly evaluate the contribution of the cochlear implant to understanding speech-in-noise. On a second task, we will evaluate sound localization in a 19-loudspeaker array. Stimuli are brief speech sounds; the overall level is roved and the spectrum is roved within a critical band to eliminate monaural level and spectral cues. Listeners identify the location of the loudspeaker emitting the sound, and testing is done in quiet, and with background noise at SNRs that vary from negative to positive values. Data are analyzed to yield root mean square error for localization, patterns of localization within a hemifield and across a hemifield, as is standard in the [name] lab ([name] et al., 2006; 2009).

2.2 Secondary Objective(s)

SSD patients with significant tinnitus will be identified using the Tinnitus Handicap • Inventory (THI) questionnaire, which is a validated measure of the degree to which tinnitus can adversely affect patients. The THI administered preoperatively and at 3, 6 and 12 month intervals following CI surgery will provide a primary measure of tinnitus relief. A secondary measure, obtained at the same time points, will be tinnitus loudness (1) rated by the patient on a 0 - 10 scale and (2) measured as the level of sound stimulation of the hearing ear needed to match the loudness of the sound to that of the tinnitus. Auditory brainstem responses (ABR) to monaural sound stimulation of the hearing ear (specifically wave V amplitude) will be measured preand 6 months post-operatively to test whether CI use reverses previously-documented brainstem hyperactivity related to tinnitus (Gu et al., 2012; Schaette and McAlpine, 2011).

3. STUDY DESIGN

3.1 Study Design Description

The study of the MAESTRO Cochlear Implant system in patients with single sided deafness will be conducted as a prospective study with ten patients undergoing cochlear implantation (ten patients total). Pre-operative baseline measures will be obtained as outlined below. Post-operative evaluations will be conducted at initial device activation, and three, six, and twelve months post-activation. Because the presence or absence of a cochlear implant is easily recognized from visual inspection, blinding and masking procedures will not be utilized as part of the study design. The safety of the implant will be determined by monitoring major and minor complications in the cohort of study participants.

Candidates that are suitable for surgery will undergo placement of a cochlear implant. The cochlear implant wires will then be placed in the cochlea and tested intra-operatively. After confirmation of optimal electrode array placement, the receiver will be implanted within the temporal bone posterior to the pinna. The overlying subcutaneous tissue and skin will then be closed and covered with dressings using standard surgical techniques. Intra-operative imaging with a reverse Stenver X-ray will be performed to confirm proper electrode placement.

Following surgical implantation of the MAESTRO Cochlear Implant and two to three weeks of healing, the device will be activated and auditory performance will be assessed at the time of activation and at three, six, and twelve months post-activation. Subjects will be evaluated with the prior approved cochlear implant speech processor programmed with an approved sound-processing algorithm. Post-operative auditory function will be tested with a battery of pure tone threshold audiometry, word recognition testing, and spatial hearing testing. The degree of tinnitus present will be assessed using the Tinnitus Handicap Inventory.

The detailed list of assessments includes:

Prior to Surgery

Important baseline and control tests will be performed pre-operatively to obtain data for comparison. These will include:

 Modified Hearing Handicap Inventory and Quality of Life (SF-36) questionnaires will be administered (see attached)

- Tinnitus Handicap Index and Auditory Brainstem Response (ABR) testing
- Psychophysical measures

• Spatial hearing testing at the Binaural Hearing and Speech Lab at the University of Wisconsin - Madison ([name] lab)

Initial Activation

Approximately four weeks post-operatively, subjects will be fitted with an approved MED-EL Sound Processor and initial stimulation will take place. The following procedures will occur at this visit:

- Modified Hearing Handicap Inventory and Quality of Life (SF-36) questionnaires will be administered (see attached)
- Detection measures
- Psychophysical measures
- Safety measures

Three, Six, and Twelve Months Post-activation Visits (to MEEI):

The following procedures will occur at all these visits unless otherwise specified:

 Modified Hearing Handicap Inventory and Quality of Life (SF-36) questionnaires will be administered (see attached)

- Pure tone threshold audiometry at each post-activation interval
- Word recognition testing at each post-activation interval
- Tinnitus assessment at each post-activation interval, along with ABR testing at the six month mark
- Psychophysical measures at each post-activation interval
- Safety measures at each post-activation interval

Visit to University of Wisconsin – Madison after Twelve Months Post-activation:

Once time has been established to acclimate to the cochlear implant, subjects will undergo study-related spatial hearing testing in addition to clinical follow up visits. Depending on subject availability in schedule, the following procedure will take place unless otherwise specified:

 $\cdot\,$ Spatial hearing testing at the Binaural Hearing and Speech Lab at UW – Madison ([name] lab)

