3.2.1 Randomization Procedures: N/A

3.2.2 Masking Procedures: N/A

• **3.2.3 Breaking the Mask**: N/A

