7.2 Enrollment/Baseline Procedures

All baseline procedures will be completed at the time of screening. This includes qualitative measurement using the Modified Hearing Handicap Inventory, Abbreviated Profile of Hearing Aid Benefit (APHAB), the Speech Spatial and Qualities of Hearing Scale (SSQ) and Quality of Life (SF-36) questionnaires as well as audiologic tests such as Early Speech Perception Testing and Consonant-Nucleus-Consonant testing. The degree to which tinnitus in the non-hearing ear affects the participant's well-being will be assessed using the Tinnitus Handicap Inventory. Auditory Brainstem Response (ABR) will be measured in patients with tinnitus as an additional clinical correlation, conducted for research purposes. Finally, patients will travel to the Binaural Hearing and Speech Lab at the University of Wisconsin – Madison for hearing-in-noise and spatial hearing testing pre- and post-operatively (see below). All costs for airfare, accommodations, meals and a daily stipend will be covered by funding from [name] laboratory.

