8.2 Effectiveness Assessments

Effectiveness assessments will be completed based on audiologic testing and subjective questionnaires at each follow-up appointment. These will be compared to the subjects' preoperative baseline measures. In particular, primary dependent measures will include:

- Pure Tone Threshold Audiometry
- Sound Localization Testing (University of Wisconsin Madison)
- Speech Perception Measures Consonant-Nucleus-Consonant (CNC) Testing
- Psychophysical Measures
- Tinnitus Assessment Tinnitus Handicap Inventory (THI)
- Subjective Questionnaires Hearing Handicap Inventory, Abbreviated Profile of Hearing Aid Benefit (APHAB) questionnaire, Speech Spatial and Qualities of Hearing Scale (SSQ), and Quality of Life (SF-36) questionnaire

Each CI subject's speech perception ability will be ranked on a continuum of performance by using standardized speech perception tests that document the range of perception abilities. We will use the Consonant-Nucleus-Consonant (CNC) test (House Ear Institute). The CNC open set single-syllable test will be administered and scored both for whole-word and phonemic items. All speech tests will use recorded materials at a level of 65dB HL and will be presented in the soundfield through a speaker to the subject at 0 degree azimuth and calibrated at a set

distance, typically 1 meter. We will test SSD patients in the bilateral condition, using the good ear only and use contralateral masking to eliminate contributions from the good ear to evaluate the implanted ear.

Each subject's spatial hearing ability will be assessed in collaboration with [name] at the University of Wisconsin. Subjects will identify a single word randomly chosen from a set of fifty possibly alternatives and presented from a loudspeaker directly in front of the subjects. Speech intelligibility will be tested by masking sentences co-presented at different spatial configurations. The presentation level of the target speech will be varied in order to generate different signal-to-noise ratios at each condition. We will evaluate implanted SSD patients with the device turned on and off to directly evaluate contribution of the cochlear implant to understanding speech-in-noise.

Recorded test materials, test keys and patient response forms will be collected and documented as part of the study. Number of test items and percentage scores on each test will be documented and included in the data analysis.

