10.7 Interim Analyses

• Interim analyses will be completed once three, five, and eight patients are enrolled. These analyses will be completed at six months and one year post-operatively for each of these cohorts. Study staff and the Investigator will perform the interim analyses, and results will be shared with the HSC through routine study renewal forms. If significant concerns arise regarding safety of the proposed device, these analyses will be shared with the HSC within 7 days and appropriate discussion to follow. Of note, the safety concerns described here do not include adverse or unanticipated safety events, which will be handled as described in Section 9.

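### Implant visibility does not justify unmasked reading of stored ABR traces, so wave V amplitude is open to an avoidable reader lean

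*Combined protocol and SAP*

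**What the plan says.** Section 3.1 excludes masking from the whole study on a single ground: "Because the presence or absence of a cochlear implant is easily recognized from visual inspection, blinding and masking procedures will not be utilized". The dedicated section adds nothing: "3.2.2 Masking Procedures: N/A".

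Section 2.2 defines the measurement at issue: "Auditory brainstem responses (ABR) to monaural sound stimulation of the hearing ear (specifically wave V amplitude) will be measured". The two time points are before surgery and 6 months after it. The stated purpose is directional, namely to see whether implant use undoes a brainstem overactivity linked to tinnitus. Section 10.2 lists ABR beside the Tinnitus Handicap Inventory (THI) for the secondary tinnitus outcome. Section 7.2 describes its role more modestly: "Auditory Brainstem Response (ABR) will be measured in patients with tinnitus as an additional clinical correlation".

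On handling of results, Section 12.1 gives each subject a random numeric code but mentions nothing that would hide the visit. Section 10.7 says "Study staff and the Investigator will perform the interim analyses", and Section 11.1 has the investigator and staff meet every two weeks or every month to share data and discuss new analyses. No section names a masked reader for any measure.

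**The concern.** The reason in Section 3.1 is about seeing the patient. A wave V amplitude is a value taken from a recorded trace, and that step can be done away from the patient, at a later date, by someone who is not told which visit the trace came from. For this step the implant's visibility is irrelevant, so the protocol gives up a safeguard that its own argument does not require it to give up.

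If the peak and trough are marked by hand, there is room for judgement. A reader who knows that a trace is post-operative also knows which way the study hopes it will move. THI and the loudness ratings and matches all depend on the responses of a patient who knows about the implant. ABR depends least on the patient, so it is also where masking is most practicable. Section 10.1 relies on having objective as well as subjective data, and unmasked reading weakens the objective part for no gain.

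**Working it through.** **Inputs**
- Ten subjects (Section 10.3).
- Two ABR recordings per subject, pre-operative and 6 months (Sections 2.2 and 3.1).
- ABR in patients with tinnitus (Section 7.2). Tinnitus is also listed among the inclusion criteria (Section 4.1).
- Unnamed non-parametric tests, p ≤ 0.05, sidedness not given (Section 10.5).
- No SD, effect size or power figure (Section 10.3), so there is no stated figure to reproduce.

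**Number of readings.** 10 × 2 = 20 if all ten subjects have tinnitus and complete both recordings. Replacements for withdrawn subjects (Section 5.2) would add theirs.

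**Where a lean goes.** Write the marked amplitude as the true amplitude plus a reading error: M0 = A0 + b0 before surgery and M6 = A6 + b6 at 6 months. Then

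M6 − M0 = (A6 − A0) + (b6 − b0).

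A reader who always marks high or always marks low has b0 = b6, and the error cancels. Only the part of the error that depends on the visit survives, and there is no control arm in which the same part could be estimated and subtracted. If the reader cannot tell the visit, b has the same expectation at both visits, and the expected value of b6 − b0 is zero.

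**What a lean could do to a test.** This is an illustration only. The assumptions are a group-level exact two-sided Wilcoxon signed-rank test, normal paired differences, no true change, and a lean expressed in SDs of the paired differences. At n = 10 the rejection region is a rank sum of at most 8 or at least 55 − 8 = 47, with attained level 0.0488. At n = 8 (two subjects without both recordings) it is at most 3 or at least 36 − 3 = 33, with attained level 0.039. Each rate is from 200,000 simulated samples.

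| Lean (SD) | Rejection rate, n = 10 | Rejection rate, n = 8 |
|---|---|---|
| 0 | 4.8% | 4.0% |
| 0.1 | 5.6% | 4.5% |
| 0.2 | 8.5% | 6.3% |
| 0.3 | 13.1% | 9.1% |
| 0.5 | 28.2% | 19.1% |

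Masked reading would bring the part of the lean that arises at reading back to the first row. Section 10.5 says that results are analysed subject by subject; on that approach there is no rejection rate to quote, and the lean simply sits inside each subject's difference.

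**What the protocol leaves open.** It does not say who marks wave V, whether marking is manual or automatic, or whether the implant is on or off during the recording.

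**The case against.** The strongest reply is that this is one supportive measure in an open, ten-patient study. Section 2.2 makes THI the main measure of tinnitus relief. THI, the loudness ratings and the other questionnaires are answered by patients who know they have an implant, and masked trace reading leaves their bias untouched. That stands, and it limits the importance of the point. It does not make the visibility argument apply to stored traces.

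A second reply is that marking may be automatic. If a fixed algorithm is used without manual correction, most of the concern goes, but the protocol does not say so.

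A third is that Section 10.2 promises a comparison with patients who are not implanted. Nothing shows that those patients would have ABR at two visits marked by the same reader, so the comparison cannot be counted on to remove a lean.

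A reader might also infer more than the documents support:
- *That CNC word scores should be masked in the same way.* Section 8.2 says "The CNC open set single-syllable test will be administered and scored both for whole-word and phonemic items" and "Recorded test materials, test keys and patient response forms will be collected and documented as part of the study". It does not say that scoring is done later from the forms, or that the subject's responses are recorded. If answers are judged in the session, the form already holds an unmasked judgement. Baseline CNC decides eligibility (Sections 4.1 and 4.2), so it must be scored with the subject identified. Follow-up audiologic tests are used to confirm activation (Section 7.3). In the implanted ear, baseline is at most 20%, so a large gain would itself reveal the visit.
- *That study staff do read the traces knowing the visit and the interim results.* Section 10.7 plans 3 cohorts × 2 time points = 6 interim analyses by study staff and the investigator, but nothing identifies them as the ABR readers.

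**Conclusion.** The point holds for wave V amplitude. The only reason given for having no masking does not reach the reading of stored traces, and no section provides masked reading. Up to 20 readings are exposed. The protocol therefore allows a visit-linked lean; it does not show that one will occur, and its size cannot be worked out from the documents. The false-positive rates above rest on an assumed test, assumed normality and assumed sizes of lean.

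It would be wrong to conclude that the tinnitus result stands or falls on ABR, since the protocol treats ABR as supportive. It would also be wrong to conclude that masked reading makes the study's efficacy evidence unbiased. This is a modest improvement, worth making because it is cheap and needs no change to sample size, significance level, visits or procedures.

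**What to change.** 1. In Sections 3.1 and 3.2.2, limit the no-masking statement to subjects and to the administration of tests.
2. State who marks wave V and whether marking is manual or automatic.
3. Have the existing research assistant export the ABR traces under a random code, without subject, date or visit. The person holding the code should not be the reader.
4. Have the usual reader mark all baseline and 6-month traces in one shuffled batch after the last 6-month recording. Lock the values, then break the code.
5. State the device status during ABR, because stimulation artefact could reveal a post-operative trace.

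The cost is protocol wording and some file handling, with no extra reader, visit or procedure. The downside is that ABR amplitudes are not available to the interim analyses in Section 10.7. That loss is small: the only escalation rule there concerns safety, Section 13.2 gives no criteria for discontinuing the study, and Section 7.2 says that ABR is done for research purposes.
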